5.3 Dose Reduction Criteria

Subjects will reduce the dose of medication at any time by the schedule below in the event that plasma iPTH is confirmed to be <30 pg/mL, corrected serum calcium is confirmed to be >10.3 mg/dL, or serum phosphorus is confirmed to be >5.5 mg/dL. Subjects will suspend dosing if plasma iPTH is confirmed to be <15 pg/mL or corrected serum calcium is confirmed to be >11.0 mg/dL, and will resume when plasma iPTH is \geq 30 pg/mL and corrected serum calcium is <9.8 mg/dL per the dose schedule below.

Dose reduction:

CTAP101: decrease to 30 mcg per day (from 60 mcg per day)

IR calcifediol: hold Day 29 dose

Cholecalciferol 300,000 IU: hold Day 29 dose

Paricalcitol: decrease dose to 1 mcg per day (from 2 mcg per day).

Cholecalciferol 800 IU will not be adjusted during the study period

In the event that a dose reduction is required for a subject receiving the minimum dosage of CTAP101 Capsules (30 mcg per day) or paricalcitol (1 mcg per day), the subject will suspend dosing and resume when iPTH is \geq 30 pg/mL and corrected serum calcium is <9.8 mg/dL at the same minimum dosage.

Dose resumption:

CTAP101: 30 mcg per day

Paricalcitol: 1 mcg per day

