Paricalcitol 1 mcg per day

Duration of Treatment:

Subjects will participate in the study for up to approximately 14 weeks (1 week for screening, 4 weeks for washout (if required), 1 week for BL, and 8 weeks for treatment).

Primary Efficacy Endpoint:

This study is descriptive and no primary or secondary efficacy endpoints are defined.

Descriptive analysis and plots will be created of serum calcifediol, CCI [REDACTED]

[REDACTED]
[REDACTED]
[REDACTED]
[REDACTED]
[REDACTED]

Primary Safety Endpoints:

Safety and tolerability of each medication will be evaluated in the Safety population by AEs, PEs, VS, and hematology and clinical chemistries.

Pharmacokinetic CCI Endpoints:

The following PK parameters will be calculated using observed and BL-adjusted serum calcifediol CCI concentrations: area under the concentration curve (AUC), maximum concentration, (C_{max}), time to maximum concentration (t_{max}), steady-state concentration (C_{ss}), time to steady-state concentration (t_{ss}), terminal elimination half-life ($t_{1/2}$), clearance (CL/F), and volume of distribution (Vd/F), as feasible.

CCI

Secondary Safety Endpoints:

The number (n, %) of subjects with hypercalcemia (two consecutive visits with serum calcium greater than 10.3 mg/dL) or hyperphosphatemia (two consecutive visits with serum phosphorus greater than 5.5 mg/dL) will be calculated.

Sample Size Estimation:

No formal sample size estimation has been performed for the study.

Statistical Analyses:

Descriptive statistical plan will be specified in an accompanying SAP.

Primary safety analyses will be conducted in the Safety population.

Secondary safety analyses will calculate the number and percentage of subjects in each treatment group with confirmed corrected serum calcium or serum phosphorus values above 10.3 mg/dL and 5.5 mg/dL, respectively.

Inclusion Criteria

Each subject must meet the following criteria to be enrolled in this study:

1. Be at least 18 years of age.
2. Have stage 3 or 4 CKD (estimated glomerular filtration rate (eGFR) of ≥ 15 to < 60 mL/min/1.73m² using the Modification of Diet in Renal Disease equation).
3. Be without any disease state or physical condition that might impair evaluation or which, in the Investigator's opinion, would interfere with study participation, including:
 - a. Serum albumin ≤ 3.0 g/dL;

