6.4.2 Sample Collection, Storage, and Shipping

Missed blood and urine samples should not be redrawn or recollected (unless the Investigator considers the sample necessary for subject safety) and should be noted as “not done” in source documentation along with a reason.

A central laboratory experienced in clinical research trials will be utilized. Collection, processing, storage and shipping procedures will be performed in accordance with the instructions provided by the central laboratory. Detailed instructions will be provided separately from this protocol in the laboratory manual. Blood and urine samples will be collected and analyzed for clinical laboratory tests. During the entire study, approximately 870 mL of blood will be drawn. Additional blood draws may be needed for any additional, unscheduled visits which are medically necessary.

Blood samples for measurement of certain clinical laboratory tests will be collected and shipped to the central laboratory. The central laboratory will ship the frozen specimens to the designated analytical facilities as detailed in the laboratory manual.

Samples are to be shipped to the central laboratory for each subject as visits are completed. The Investigator will provide a limited access, temperature monitored space for the study drug and a -80°C freezer space for respective serum and plasma aliquots.

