6.8 Removal of Subjects from the Study or Study Drug (Early Termination)

The Investigator may withdraw a subject from the study for any of the following reasons:

- A major protocol deviation occurs;
- A serious or intolerable AE occurs;
- A clinically significant change in a laboratory parameter occurs;
- The sponsor or Investigator terminates the study;
- The subject requests to be discontinued from the study;
- If the Investigator believes it is no longer in the best interests of the subject to continue;
- A subject becomes pregnant;

No subject replacement is planned.

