7.2.4 Visit 10 (Day 29)

- Subjects admitted into the phase 1 unit (for approximately 14 to 26 hours) after an overnight fast unless Subject chooses to stay overnight. Subjects opting to remain in the phase 1 unit

for overnight will have 24 hour read completed. Those who do not opt to stay overnight, advance to Visit 11.

- Dosing compliance and dosing diary assessed for subjects assigned to CTAP101 Capsules and paricalcitol capsules plus low-dose cholecalciferol.
- Subjects will receive standardized meals while housed in the phase 1 unit. These meals will contain 400 mg of elemental calcium and will be administered at approximately 2 (breakfast), 6 (lunch), and 10 (dinner) hours post-dose.
- Review of concomitant medications
- VS assessment
- Pre-dose blood samples will be drawn for the following:
 - Clinical chemistry (full panel) and hematology
CCI [REDACTED]
- Blood samples will be drawn from subjects housed in the phase 1 unit at approximately 6:00 a.m. ($t=$ ~2 hours), and 8:00 a.m. ($t=$ ~0 hours) and precisely (plus or minus 5 minutes, with exact time noted) at $t=$ 2, 4, 6, 12 and 24 hours (for subjects opting overnight stays) post-dose for the following analyses:
 - Clinical chemistry (partial panel)
CCI [REDACTED]
 - Serum calcifediol, **CCI** [REDACTED]
 - Additional blood samples will be drawn from subjects housed in the phase 1 unit at approximately 8:00 a.m. ($t=$ ~0 hours) and precisely (plus or minus 5 minutes, with exact time noted) at $t=$ 12 and 24 hours (for subjects opting overnight stays), post-dose for the following analysis:
CCI [REDACTED]
- AE assessments will be completed at each timed blood draw (n=6)
- Subjects take next dose of study drug with a sufficient quantity of a non-alcoholic beverage to enable swallowing of the capsules immediately after the $t=$ 0 blood draw, with the exact time of dosing noted.
- Subjects will be discharged from the phase 1 unit after the blood draw at 12 hours post-dose.
- Balance of monthly study drug supply dispensed at discharge to subjects assigned to CTAP101 Capsules and paricalcitol capsules plus low-dose cholecalciferol.

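### In the two monthly arms, Protocol 5.3 requires no confirming result before the Day 29 dose, so a safety limit first crossed on Day 22 does not by itself hold that dose

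*Protocol*

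**What the plan says.** Protocol 5.3, repeated in the synopsis and SAP 3.3, sets three reduction triggers: a low iPTH, or "corrected serum calcium is confirmed to be >10.3 mg/dL, or serum phosphorus is confirmed to be >5.5 mg/dL". The suspension triggers, which include corrected calcium above 11.0 mg/dL, must also be confirmed.

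For IR calcifediol the whole reduction schedule is "IR calcifediol: hold Day 29 dose". High-dose cholecalciferol has the same single step. Both drugs are given only on Days 1 and 29 (Protocol 5.2).

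Section 5.3 does not say what confirms a value or by when. The synopsis describes its calcium and phosphorus safety endpoint in two ways: under Statistical Analyses as "confirmed corrected serum calcium or serum phosphorus values above 10.3 mg/dL and 5.5 mg/dL, respectively", and under Secondary Safety Endpoints, for calcium, as "two consecutive visits with serum calcium greater than 10.3 mg/dL".

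At the Day 29 visit, Protocol 7.2.4 has "Subjects take next dose of study drug with a sufficient quantity of a non-alcoholic beverage to enable swallowing of the capsules immediately after the" time-zero draw. It lists no step for reviewing results first. Protocol 6.4.2 adds: "Samples are to be shipped to the central laboratory for each subject as visits are completed". It gives no turnaround time.

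**The concern.** In the daily arms, a crossing confirmed late still leaves a dose to reduce the next day. In the monthly arms the reduction is available once, and 266 mcg of calcifediol or 300,000 IU of cholecalciferol cannot be taken back. If confirmation is not in hand by the morning of Day 29, the protocol's only reduction step in these arms is lost.

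The plan is stricter elsewhere. Doubling paricalcitol after four weeks requires calcium below 9.8 mg/dL, phosphorus below 5.5 mg/dL and an iPTH condition (Protocol 5.2). Resuming a suspended dose requires calcium below 9.8 mg/dL and iPTH of at least 30 pg/mL (Protocol 5.3). The second monthly dose has no such entry condition.

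The appended labels act on calcium without a confirmation step. IR calcifediol is contraindicated above 10.5 mg/dL (Appendix 2, 4.3), and the 50,000 IU product is to be stopped above 10.6 mg/dL (Appendix 3, 4.9). A single Day 22 value of, say, 10.8 mg/dL is past both, yet does not meet the hold rule in 5.3.

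**Working it through.** **Schedule check.** This uses the chemistry days in Protocol section 7 and Appendix 1, and supposes that a value is confirmed at the next scheduled visit. The documents do not state this meaning for dosing. The endpoint wording only suggests it.

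| First crossing | Next scheduled chemistry | Time before the Day 29 dose |
|---|---|---|
| Day 2 | Day 3 | 26 days |
| Day 3 | Day 8 | 21 days |
| Day 8 | Day 15 | 14 days |
| Day 15 | Day 22 | 7 days |
| Day 22 | Day 29 (about -2 h and 0 h) | 0 to 2 hours |

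Only the last row fails. A scheduled result could confirm a Day 22 crossing in time only if the central laboratory reported within about two hours, and no text says that it does. An unscheduled repeat in the seven days from Day 22 to Day 29 would close the gap, but none is required. The check covers calcium and phosphorus, which are in the partial panel. The iPTH sampling schedule is not visible in the public documents.

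**How many subjects.** The plan gives no trigger rate for these doses, so the inputs below are assumptions.
- Monthly-arm subjects: about 2 x 20 = 40.
- p, the share who first cross a limit before Day 29: 1% to 20% (assumed).
- s, the share of first crossings that fall on Day 22: 1/5 if equally likely on Days 2, 3, 8, 15 and 22; 1/3 if equally likely on Days 8, 15 and 22 (assumed).

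Expected number = 40 x p x s:
- p = 1%: 0.08 to 0.13
- p = 5%: 0.40 to 0.67
- p = 10%: 0.80 to 1.33
- p = 20%: 1.60 to 2.67

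This is an upper bound for each p. It counts Day 22 values that a repeat would not have confirmed, and it supposes that no site repeats the test.

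**What one dose adds.** Take a one-compartment model, equal doses and baseline-adjusted 25D3. Let r = AUC(28-56 d) / AUC(0-28 d) after one dose. For a bolus, r = 2^(-28/half-life). Exposure over Days 29 to 57 with the second dose given, relative to held, is (1 + r)/r.

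| Half-life (source) | r | Given / held |
|---|---|---|
| 18 d (Appendix 2, 5.2) | 0.340 | 3.94 |
| 21 d (Appendix 2, 5.2) | 0.397 | 3.52 |
| 30 d (Protocol 3.2, CTAP101 repeat dosing) | 0.524 | 2.91 |
| 50 d (Appendix 4, 5.2) | 0.678 | 2.47 |
| 50 d with a 7-day peak (Appendix 4, 5.2; formation rate 0.536/day) | 0.738 | 2.36 |

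The ratio is about 2.9 to 3.9 for IR calcifediol and 2.4 to 2.5 for cholecalciferol. It describes 25D3 exposure only, not calcium or harm.

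**The case against.** Four points can fairly be made for the plan.

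- **The meaning of confirmed.** Section 5.3 is a dosing rule that applies at any time and mentions no visits. An ordinary repeat test fits it, and Protocol 6.4.2 provides for one: "Additional blood draws may be needed for any additional, unscheduled visits which are medically necessary". SAP 9.3 counts one as well as two consecutive visits, so the endpoint does not settle the dosing term. This stands: the two-visit meaning cannot be read into 5.3 as a definition.
- **Follow-up duties.** Clinically significant laboratory values are recorded as AEs and followed up (Protocol 6.4.1, 6.6.3), and an abnormality counts as significant unless the investigator marks it otherwise (6.6.6). Section 6.8 lets the investigator withdraw a subject when "A clinically significant change in a laboratory parameter occurs". The labels are appended to the protocol, so the investigator has their limits to hand. All this makes an unheeded high calcium less likely. But AE follow-up prescribes no repeat by Day 29, withdrawal is optional and is not a dose hold, and 5.3 does not incorporate the label limits.
- **Results around Day 29.** The paricalcitol decision needs laboratory results at about that visit, and sample handling is detailed in a separate laboratory manual. Results may well be reviewed in practice. The protocol does not make it a condition of dosing in the monthly arms.
- **Harm.** The IR calcifediol label recommends weekly or fortnightly capsules in renal osteodystrophy (Appendix 2, 4.2), so a second monthly capsule is not excessive in itself. That is true, but the same label contraindicates it above 10.5 mg/dL. The label argument concerns calcium only, not phosphorus or iPTH.

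A reader might infer that a subject who crosses on Day 22 will be dosed, or that the confirming result necessarily arrives after the dose. The documents support neither: sites may repeat the test, and the turnaround is unstated rather than known to be long.

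**Conclusion.** The point holds as a gap in the dosing rule. In both monthly arms the one available reduction depends on confirmation that nothing requires to be in hand before the dose, so a limit first crossed on Day 22 does not by itself hold it. This rests on the text of 5.3, 7.2.4 and 6.4.2, and on the absence of any instruction elsewhere to repeat or hold. Requiring confirmation before changing a dose is a legitimate choice. What is missing is a step that secures it in time.

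The size is small: a fraction of a subject to under three of about 40, as an upper bound on assumed rates. The consequence for any such subject is one irreversible dose. The change is worth making because it is cheap and improves safety, but it does not threaten the trial's analysis.

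**What to change.** Add to Protocol 5.3, the synopsis dosing plan and SAP 3.3:

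> In the IR calcifediol and high-dose cholecalciferol arms, if the most recent corrected calcium, phosphorus or iPTH before Day 29 is beyond a reduction limit and is not yet confirmed, it is repeated at an unscheduled draw and the result is reviewed before the Day 29 dose. The dose is omitted if the repeat confirms the value, if no repeat result is available, or if the most recent corrected calcium is above 10.5 mg/dL. Values already followed by a within-limit result need no repeat. An omitted dose is not given later.

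The third sentence spares subjects whose early high value has already been cleared. The 10.5 mg/dL condition keeps dosing within the stricter label limit however confirmation is read.

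The cost is one extra draw per flagged subject and, if the repeat is missed, possible loss of that subject's second-dose PK in an arm of about 20. The analysis does not change, because SAP 7.1 and 7.2 already present dose-adjusted subjects as a subgroup.

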Approximately 80 subjects will be randomized 1:1:1:1 (approximately 20 per arm) to receive one of the listed study medications with a sufficient quantity of a non-alcoholic beverage to enable swallowing of the capsules:

- 1) CTAP101 Capsules 60 mcg once daily outside of the phase 1 unit at bedtime, except on Days 1 and 29 when dosing will occur in the phase 1 unit in the morning before breakfast.
- 2) IR calcifediol 266 mcg in the phase 1 unit before breakfast on the mornings of Day 1 and Day 29.
- 3) Cholecalciferol 300,000 IU (high-dose) in the phase 1 unit before breakfast on the mornings of Day 1 and Day 29.
- 4) Paricalcitol 1 mcg plus cholecalciferol 800 IU (low-dose) once daily outside of the phase 1 unit in the morning before breakfast, except on the mornings of Days 1 and 29 when dosing will occur in the phase 1 unit before breakfast.

After 4 weeks of treatment, subjects who are receiving paricalcitol will double the dose to 2 mcg plus cholecalciferol 800 IU once daily in the morning before breakfast provided that (a) the plasma iPTH has not decreased by at least 30% from pretreatment BL and remains above 70 pg/mL, (b) corrected serum calcium is <9.8 mg/dL, and (c) serum phosphorus is <5.5 mg/dL. Subjects who are receiving CTAP101 Capsules, IR calcifediol or cholecalciferol (300,000 IU) will not undergo upward dose titration.

Subjects will reduce the dose of study medication per the schedule below in the event that plasma iPTH is confirmed to be <30 pg/mL, corrected serum calcium is confirmed to be >10.3 mg/dL, or serum phosphorus is confirmed to be >5.5 mg/dL. Subjects will suspend dosing if plasma iPTH is confirmed to be <15 pg/mL or corrected serum calcium is confirmed to be >11.0 mg/dL, and will resume dosing when plasma iPTH is ≥30 pg/mL and corrected serum calcium is <9.8 mg/dL per the dose schedule below.

Dose reduction (if needed):

CTAP101: decrease to 30 mcg per day (from 60 mcg per day)

IR calcifediol: hold Day 29 dose

Cholecalciferol 300,000 IU: hold Day 29 dose

Paricalcitol: decrease dose to 1 mcg per day (from 2 mcg per day)

Cholecalciferol 800 IU will not be adjusted

In the event that a dose reduction is required for a subject receiving the minimum dosage of CTAP101 Capsules (30 mcg per day) or paricalcitol (1 mcg per day), the subject will suspend dosing and resume when iPTH is ≥ 30 pg/mL and corrected serum calcium is <9.8 mg/dL at the same minimum dosage.

Dose resumption (if needed):

CTAP101: 30 mcg per day

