5 STUDY TREATMENTS

5.1 Description of Study Medications

Five study medications will be used in the execution of this protocol which are described in sections 5.1.1 through 5.1.5. All study medications will be securely stored for light and heat protection and in accordance to USP Controlled Room Temperature, defined as 20°C to 25°C (68°F to 77°F) with excursions permitted between 15°C to 30°C (59°F to 86°F).

5.1.1 *Description of CTAP101 Capsules*

Dosage form: Soft gel capsule
Dose strength: 30 mcg calcifediol ER capsule
Product description: Blue oval capsules printed single-sided, centered with the logo O in white. Each bottle contains 30 capsules.
Active component: Calcifediol
Non-active components: Paraffin wax, mineral oil, mono- and diglycerides, dehydrated alcohol, lauroyl polyoxylglycerides, butylated hydroxytoluene, hypromellose, modified starch, carageenan, sodium phosphate dibasic, sorbitol and sorbitan solution, FD&C Blue #1, titanium dioxide, medium chain triglycerides (coconut oil) and ink (white, which may contain titanium dioxide, isopropyl alcohol, propylene glycol, hydroxypropylmethyl cellulose 2910)

5.1.2 *Description of Calcifediol IR Capsules*

Dosage form: Soft gel capsule
Dose strength: 266 mcg calcifediol IR capsule
Product description: Orange capsule. Each Al-Al blister or PVC/PVDC-Al blister pack carton contains 10 capsules.
Active component: Calcifediol
Non-active components: Absolute anhydrous ethanol, medium chain triglycerides, gelatin, vegetable glycerin, sorbitol (70%) (E-420), titanium dioxide (E-171), yellow-orange dye S (E-110) and purified water.

For product information, refer to [APPENDIX 2](#).

5.1.3 *Description of High-Dose Cholecalciferol Capsules*

Dosage form: Soft gel capsule
Dose strength: 50,000 IU cholecalciferol capsule
Product description: Red, oval-shaped capsule with “50” printed in white ink. Each PVDC/aluminum foil blister pack with cardboard carton contains 3 capsules.

Active component: Cholecalciferol
Non-active components: All-rac- α -tocopherol (E307), medium chain triglycerides, glycerol, gelatin, Allura Red AC (E129), Opacode® white imprinting ink, shellac (E904), titanium dioxide (E171) and simethicone.

For product information, refer to [APPENDIX 3](#).

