5.2 Dosing Plan

Approximately 80 subjects will be randomized 1:1:1:1 (approximately 20 per arm) to receive one of the listed study medications with a sufficient quantity of a non-alcoholic beverage to enable swallowing of the capsules:

- 1) CTAP101 Capsules 60 mcg once daily outside of the phase 1 unit at bedtime, except on Days 1 and 29 when dosing will occur in the phase 1 unit in the morning before breakfast.
- 2) IR calcifediol 266 mcg in the phase 1 unit before breakfast on the mornings of Day 1 and Day 29.
- 3) Cholecalciferol 300,000 IU (high-dose) in the phase 1 unit before breakfast on the mornings of Day 1 and Day 29.

4) Paricalcitol 1 mcg plus cholecalciferol 800 IU (low-dose) once daily outside of the phase 1 unit in the morning before breakfast, except on Days 1 and 29 when dosing will occur in the phase 1 unit before breakfast.

After 4 weeks of treatment, subjects who are receiving paricalcitol will double the dose to 2 mcg plus cholecalciferol 800 IU once daily in the morning before breakfast provided that (a) the plasma iPTH has not decreased by at least 30% from pretreatment BL and remains above 70 pg/mL, (b) corrected serum calcium is <9.8 mg/dL, and (c) serum phosphorus is <5.5 mg/dL. Subjects who are receiving CTAP101 Capsules, IR calcifediol or cholecalciferol (300,000 IU) will not undergo upward dose titration.

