4.9 Overdose

Overdose can lead to hyper-vitaminosis D. An excess of vitamin D causes abnormally high levels of calcium in the blood, which can eventually severely damage the soft tissues, and kidneys.

Tolerable Upper Intake Level for vitamin D3 (colecalciferol) is set at 4000 IU (100 µg) per day.

Vitamin D3 should not be confused with its active metabolites. colecalciferol

Symptoms of hypercalcaemia may include anorexia, thirst, nausea, vomiting, constipation, abdominal pain, muscle weakness, fatigue, mental disturbances, polydipsia, polyuria, bone pain, nephrocalcinosis, renal calculi and in severe cases, cardiac arrhythmias. Extreme hypercalcaemia may result in coma and death.

[figure not shown]
Persistently high calcium levels may lead to irreversible renal damage and soft tissue calcification.

Treatment of hypercalcaemia: The treatment with vitamin D must be discontinued. Treatment with thiazide diuretics, lithium, vitamin A, and cardiac glycosides must also be discontinued. Rehydration, and, according to severity, isolated or combined treatment with loop diuretics, bisphosphonates, calcitonin and corticosteroids should be considered. Serum electrolytes, renal function and diuresis must be monitored. In severe cases, ECG and CVP should be followed.

5. Pharmacological properties

5.1

CCI

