Subjects will suspend dosing if plasma iPTH is confirmed to be <15 pg/mL or corrected serum total calcium is confirmed to be >11.0 mg/dL, and will resume dosing when plasma iPTH is  $\geq$ 30 pg/mL and corrected serum total calcium is <9.8 mg/dL per the following schedule. In the event that a dose reduction is required for a subject receiving the minimum dosage of CTAP101 Capsules (30 mcg per day) or paricalcitol (1 mcg per day), the subject will suspend dosing and resume when iPTH is  $\geq$ 30 pg/mL and corrected serum total calcium is <9.8 mg/dL at the same minimum dosage.

Dose resumption (if needed):

CTAP101: 30 mcg per day

Paricalcitol 1 mcg per day

The subjects will be housed in a phase 1 unit for approximately 14 to 26 hours at the beginning of the study and on study Day 29 to provide the blood samples required for a detailed determination of the PK profiles for serum calcifediol [REDACTED]

[REDACTED] Blood samples for some of the PK and [REDACTED] assessments will be collected in the phase 1 unit at -2, 0, 2, 4, 6, and 12 hours, either in the phase 1 unit or during an outpatient visit at 24 hours, during the outpatient visit at 48 hours, and then weekly following the first dose and the Day 29 dose of study drug. Blood samples for other [REDACTED] assessments will be collected at less frequent intervals. Urine collections (over 24 hours) will be obtained at pretreatment BL (Visits 2 and 3), starting immediately after dosing on Day 1 (Visit 4) and Day 29 (Visit 10), and at the end of study (EOS) visit

(Visit 16) or at early termination (ET). The full schedule of assessments is provided in Table 1.

Subjects receiving treatment with calcitriol or another 1 $\alpha$ -hydroxylated vitamin D analog, or if serum total 25D >30 ng/mL when taking vitamin D supplementation (including multivitamins and fish oil), will complete a 4-week washout period before BL assessments. Subjects will forgo further dosing with these nonstudy drugs for the duration of the study. Subjects receiving calcimimetic therapy within the 12 weeks preceding Screening will be ineligible for enrollment.

Blood samples will be collected from all subjects at weekly intervals during the screening and BL periods, during the 8-week treatment period, and at the specified times during the PK/CCI assessment. Key parameters to be analyzed in the collected samples include some or all of the following: serum calcifediol, CCI [REDACTED]

[REDACTED] serum 24,25D3, CCI [REDACTED]

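### As written, cholecalciferol 800 IU continues while paricalcitol is suspended for confirmed hypercalcemia, which conflicts with the protocol's own product information at calcium above 11.0 mg/dL

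*Protocol*

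**What the plan says.** Arm 4 subjects take two products daily. All of them start on paricalcitol 1 mcg with cholecalciferol 800 IU. Under Protocol 5.2, "After 4 weeks of treatment, subjects who are receiving paricalcitol will double the dose to 2 mcg plus cholecalciferol 800 IU once daily", if the iPTH, calcium and phosphorus conditions are met.

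Protocol 5.3 has two suspension rules.

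- At any dose: "Subjects will suspend dosing if plasma iPTH is confirmed to be <15 pg/mL or corrected serum calcium is confirmed to be >11.0 mg/dL".
- At the lowest dose, any reduction trigger becomes a suspension. The triggers are confirmed iPTH <30 pg/mL, corrected calcium >10.3 mg/dL or phosphorus >5.5 mg/dL. The sentence covers subjects on CTAP101 30 mcg "or paricalcitol (1 mcg per day), the subject will suspend dosing and resume when iPTH is" and calcium are back within limits, at that same lowest dose.

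The one line specific to the low-dose capsule stands in the dose-reduction list: "Cholecalciferol 800 IU will not be adjusted during the study period". The synopsis and SAP 3.3 carry the shorter form, "Cholecalciferol 800 IU will not be adjusted". The resumption list, in all three places, names CTAP101 and paricalcitol only.

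Appendix 4 section 4.9, the product information for the 800 IU capsule, states: "Treatment of hypercalcaemia: The treatment with vitamin D must be discontinued". Appendix 3 section 4.9, for the 50,000 IU capsule of the same substance, says to stop it once calcium exceeds 10.6 mg/dL.

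**The concern.** A stopping rule for hypercalcemia should not leave a vitamin D product running without a stated reason. Here the active analog is stopped for high calcium while the nutritional vitamin D in the same arm goes on, in patients with stage 3 or 4 CKD. The product information attached to the protocol points the other way, and 5.3 neither refers to it nor explains the departure.

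A secondary matter is compliance. SAP 9.7 compares capsules taken with capsules that should have been taken, and Protocol 5.6 makes compliance below 80% a deviation. If the capsule is meant to continue, a site that holds it out of caution can generate a deviation.

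**Working it through.** The plan gives no figure on this point, so there is none to reproduce. The check is textual, followed by rough sizing.

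**1. Which product stops.** The lowest-dose sentence names CTAP101 and paricalcitol. The resumption list names the same two. The 800 IU line says no adjustment and, in 5.3, extends that to the whole study. These three agree: paricalcitol is the adjustable drug and 800 IU is fixed. Only the rule for calcium >11.0 mg/dL or iPTH <15 pg/mL names no product.

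**2. Calcium bands against the product information.**

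| Confirmed corrected calcium (mg/dL) | On paricalcitol 1 mcg | On paricalcitol 2 mcg | Product information |
|---|---|---|---|
| >10.3 to 10.6 | suspend | step down to 1 mcg | no clear threshold for cholecalciferol |
| >10.6 to 11.0 | suspend | step down to 1 mcg | Appendix 3, 4.9: stop the 50,000 IU capsule |
| >11.0 | suspend | suspend | as above; Appendix 4, 4.9: stop vitamin D in hypercalcaemia |

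Appendix 4 section 4.9 gives no calcium value, so placing it in the last row is a judgment. Appendix 2 section 4.3 uses >10.5 mg/dL, but for IR calcifediol. Because everyone in arm 4 is on 1 mcg until Day 29, confirmed calcium >10.3 mg/dL already means suspension during the first four weeks.

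**3. How many subjects.** Inputs are about 20 subjects in arm 4, 8 weeks of treatment, and hypercalcemia rates from Protocol 1.12. A constant hazard is assumed: expected number = 20 × (1 − (1 − p)^(weeks at risk / weeks observed)).

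- US phase 3 trials, 2% over 24 weeks: 20 × (1 − 0.98^(8/24)) = 0.13.
- The 2 mcg trial, nearly 23% over 8 + 40 = 48 weeks: 20 × (1 − 0.77^(8/48)) = 0.85.
- The same rate for the last 4 weeks only, with everyone up-titrated: 20 × (1 − 0.77^(4/48)) = 0.43. This leaves out the first four weeks; the 0.85 covers them at the higher dose.

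Both rates count two consecutive values >10.5 mg/dL, which matches neither trial trigger. A third rate, 43% on 1 mcg at calcium >10.2 mg/dL, has no stated duration and no stated repeat requirement, so it is not used for sizing. Borrowing the other trials' durations as an assumption, it would give 20 × (1 − 0.57^(8/24)) = 3.4 or 20 × (1 − 0.57^(8/48)) = 1.8 subjects under that looser definition. One subject or fewer is therefore an expectation, not a bound.

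**4. How much vitamin D.** Durations are assumed. One weekly visit interval: 7 × 800 = 5,600 IU. Day 15 through Day 56: 42 × 800 = 33,600 IU.

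**5. Compliance.** With 56 planned capsules, an 11-day hold gives 45/56 = 80.4% and a 12-day hold gives 44/56 = 78.6%. The second is below the 80% limit if the capsule was expected to continue. Dosing non-compliance may be a major deviation (Protocol 10.8), and major deviations remove a subject from the PK population (SAP 5.4).

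**The case against.** The best defence is that fixed background vitamin D is a deliberate choice and the label argument is thin. Section 4.9 of Appendix 4 deals with overdose, and 800 IU is the recommended daily dose (Appendix 4 section 4.2). The contraindication in section 4.3 concerns underlying conditions that cause hypercalcaemia, not a laboratory value on treatment with another drug. The 10.6 mg/dL figure belongs to the 50,000 IU capsule. These points stand as limits on how far the product information reaches. They do not explain continuing vitamin D above 11.0 mg/dL, where the protocol itself considers calcium high enough to stop paricalcitol at any dose.

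Two stronger readings are tempting.

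- *A reader might infer that 5.3 leaves it open whether the capsule is held, so that sites would split.* There is some basis: one suspension sentence names no product, the 800 IU line sits in the reduction list, and the capsule is a study drug ("Five study medications will be used in the execution of this protocol"). But the resumption list, the lowest-dose sentence and the no-adjustment line all favour continuation, and SAP 3.3 foresees at most three sites. The weight of the text is a rule, not a gap.
- *A reader might infer that the product information requires stopping at 10.3 mg/dL.* No appendix gives that threshold.

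The compliance point is also limited. SAP 9.7 lists dose diary and dosing plan data, including suspensions, for all treatments, so actual handling will be visible.

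**Conclusion.** The point holds in a limited form. Read as written, Protocol 5.3, the synopsis and SAP 3.3 keep cholecalciferol 800 IU going through a paricalcitol suspension for confirmed hypercalcemia. Above 11.0 mg/dL this conflicts with Appendices 3 and 4. From 10.3 to 10.6 mg/dL no conflict is shown, and a hold rests on consistency alone.

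The expected safety gain is small. Paricalcitol stops either way, the dose at issue is low, calcium is measured weekly, and Protocol 6.8 lets the investigator withdraw a subject for a clinically significant laboratory change. Probably one subject or fewer is affected, given a constant hazard, borrowed rates with different calcium cut-offs, and the third rate left out. Nothing here changes an endpoint definition or a statistical conclusion. This is a minor, cheap improvement.

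**What to change.** In Protocol 5.3, the synopsis and SAP 3.3, replace the 800 IU line with:

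*Cholecalciferol 800 IU has no dose-reduction step; it is held during any suspension of paricalcitol in which corrected serum calcium is confirmed >10.3 mg/dL, whatever triggered the suspension, and is resumed at 800 IU per day when paricalcitol resumes.*

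Add the capsule to the resumption list, and add a line to SAP 9.7 so that capsules held under this rule are not counted as expected.

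Tying the hold to the calcium value rather than to the trigger covers a subject already suspended for iPTH or phosphorus whose calcium then rises. The capsule still continues when calcium is not confirmed >10.3 mg/dL, and during a step-down from 2 to 1 mcg. That step-down can occur at calcium between 10.6 and 11.0 mg/dL, so the sponsor should accept that limit knowingly.

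The cost is one sentence and one list entry in three places and one line in SAP 9.7, with no new visits or data. The downside is a short interruption of nutritional vitamin D in the few subjects affected.
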